6.3. Medical History

A complete medical history will be collected at screening. Concomitant medications, recent illnesses, and participation in other investigational drug studies will also be recorded. The examinations will be performed as outlined in Schedule of Procedures and Visits ([Table 1](#)).

6.4. Physical, [REDACTED] and Neurological Examinations

6.4.1. Physical Examination

The examinations will be performed as outlined in Schedule of Procedures and Visits ([Table 1](#)). The physical examination will be performed by the investigator. It will include assessments of general appearance, skin, head (eyes, ears, nose, and throat), neck, thyroid, lungs, heart, abdomen, back, lymph nodes, and extremities, and body weight. Height will only be obtained at screening. Patients with eye disturbances indicating macular edema, such as blurred vision in combination with metamorphopsia, must be referred to an ophthalmologist for further examination.

6.4.3. Neurological Examination

The neurological examination includes assessments of the neurological system (cranial nerves, motor and sensory function, coordination, and mental status). In addition, monitoring for PML will be performed [REDACTED] using a subjective PML checklist (refer

██████████ The examinations will be performed as outlined in Schedule of Procedures and Visits (Table 1).

6.5. Vital Signs

Supine (laying face upward) blood pressure, heart rate, temperature, and respiratory rate will be measured after the patient has been resting for 5 minutes. Vitals signs will be measured prior to any blood draw or any other invasive procedure that occurs at the same visit or time point. Vital signs will be measured according to the time points in the Schedule of Procedures and Visits (Table 1). Vital signs are to be measured ██████████ of the scheduled timepoint.

6.6. Electrocardiography

6.6.1. ECG Equipment

Safety ECGs will be recorded from an ECG machine (12-lead). Safety ECGs will be printed and reviewed on-site by the PI or other physician (e.g., cardiologist). Typically, all safety ECGs will be obtained as single tracings, with the exception of the pretreatment ECG obtained on Day 1, which is a triplicate recording.

[figure not shown]
6.6.2. ECG Acquisition

[figure not shown]
[figure not shown]
The safety ECG equipment will be set according to ECG and ██████████.

6.6.3. ECG Assessment

Safety ECGs will be performed as outlined in Schedule of Procedures and Visits (Table 1). ECGs are to be measured ██████████ of the scheduled timepoint.

The PI or designee (physician) will be responsible for review and interpretation of safety ECG on-site and determining if the ECG is normal, abnormal “not clinically significant” or abnormal “clinically significant”. Abnormalities of particular interest include increased PR and QTc intervals, either absolute prolongations or clinically noteworthy increases from baseline values.

6.9. Clinical Laboratory Tests

The clinical laboratory tests will be performed as outlined in Schedule of Procedures and Visits (Table 1). Tests will be performed in the central laboratory. If the patient lives in a remote area, laboratory testing for close observation for possible DILI may be performed locally and the results promptly communicated to the clinic.

In the event of abnormal clinical laboratory values, the physician will make a judgment whether or not the abnormality is clinically significant. If clinically significant, it will be captured and recorded as an AE.

6.9.1. List of Laboratory Parameters

Laboratory tests will include the following:

Serum Chemistry

Albumin (ALB)
Alkaline phosphatase (ALP)
Alanine aminotransferase (ALT; SGPT)
Amylase
Aspartate aminotransferase (AST; SGOT)
Bicarbonate
Blood urea nitrogen (BUN)
Calcium (Ca)
Chloride (Cl)
Creatinine
Creatine kinase and MB subtype (if elevated) (% and total MB)*
Gamma-glutamyl transferase (GGT)
Glucose
Lactate dehydrogenase (LDH)
Lipase
Magnesium
Phosphate
Potassium (K)
Sodium (Na)
Total bilirubin
Direct bilirubin
Total protein

Serum Chemistry Lipid Panel

High-density-lipoprotein (HDL)
Low-density-lipoprotein (LDL)
Total cholesterol (TC)
Triglycerides (TG)

Hematology

Hematocrit (Hct)
Hemoglobin (Hb)
Lymphocyte subsets (CD4, CD8 and NK cells)
Mean corpuscular hemoglobin (MCH)
Mean corpuscular volume (MCV)
Platelet count
Red blood cell count (RBC)
White blood cell count (WBC) with differential (% and absolute counts)

Coagulation

Prothrombin time (PT)
Activated partial thromboplastin time (PTT)
International Normalized Ratio (INR)

Additional tests

[REDACTED]
Urine dipstick test
Follicle stimulating hormone (FSH)

[REDACTED]
AMA
[REDACTED]

Additional tests at screening

[REDACTED]
HBsAg
Anti-HCV
[REDACTED]
QuantiFERON
Thyroid-stimulating hormone (TSH)
Triiodothyronine (free T3)
Thyroxine (free T4)

* alternatively, this can be done by troponin test (T and or I)

6.9.3. Urinalysis

Urinalysis will follow the local practice at the study site (as dipstick). Tests will be performed as outlined in Schedule of Procedures and Visits (Table 1). Parameters for clinical laboratory tests include the following:

- appearance + color
- specific gravity
- pH
- leukocytes
- protein
- glucose
- nitrites
- ketones
- urobilinogen
- bilirubin
- blood/erythrocytes

[figure not shown]
Microscopic urinalysis will be performed when there is a positive or abnormal macroscopic urinalysis result as deemed necessary by the investigator.

6.9.4. Sample Collection

All blood and urine samples will be collected according to site standards. Tests will be performed as outlined in Schedule of Procedures and Visits (Table 1).

6.9.5. Blood Volume

The total blood volume collected from each patient participating in the study (according to the sampling described in the Schedule of Procedures and Visits [Table 1]) is estimated to be 340 mL, but will not exceed 500 mL.

6.11.1. Patient 5-D Pruritus Scale

The patient 5-D itch scale was developed as a brief but multidimensional questionnaire designed for pruritus and to be useful as an outcome measure in clinical trials as it measures changes over time. The five dimensions are degree, duration, direction, disability and distribution. This assessment sheet will be completed by the patient as per Schedule of Procedures and Visits (Table 1).

6.11.2. Patient PBC-40 Quality of Life Scale

The PBC-40 is a disease specific health related quality of life measure for PBC, scored on a scale of 1 to 5 (where 1 = least impact, 5 = greatest impact) grouped into six domains (symptoms, itch, fatigue, cognition, social, and emotional). For each domain, scoring involved summing individual question response scores. Higher scores indicate a poorer quality of life. This assessment sheet will be completed by the patient as per Schedule of Procedures and Visits (Table 1).

6.12. Hematologic Assessments

[figure not shown]
6.12.1. Complete Blood Count

Blood samples for CBC with differential and platelet count, as well as lymphocyte subsets, will be assessed. Tests will be performed as outlined in Schedule of Procedures and Visits (Table 1).

If the absolute peripheral lymphocyte count has not recovered to at least 80% of the baseline value, or within normal ranges, at the 2-week follow-up (week 26), the patient must return for weekly CBCs until the absolute peripheral lymphocyte count has returned to at least these values.

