6.15. Adverse Events Assessments

Patients will be monitored from ICF signature to 30 days after the last dose of study drug for AEs to the study drug and/or procedures.

AEs will be recorded and reported in accordance with ICH GCP. The definitions of AEs and serious AEs (SAEs) will be as given in ICH Guideline E2A, “*Clinical Safety Data Management: Definitions and Standards for Expedited Reporting*.” The outcome of an AE will be defined according to ICH Guideline E2B(R3), “*Clinical Safety Data Management: Data Elements for Transmission of Individual Case Safety Reports*.” The relationship to investigational product will be classified using World Health Organization (WHO) criteria.

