6.15.1. Adverse Event Reporting

Patients will be instructed to report all AEs, which can be reported at any time. AEs that occur from ICF signature until the time of administration of the first dose of etrasimod will be regarded as ‘pre-treatment’ and recorded as an AE. All events reported following study medication administration up to 30 days after the last medication intake will be presented as treatment emergent AEs (TEAEs).

Monitoring of ongoing AEs will be continued up to 30 days after study medication administration.

[figure not shown]
For this study, an AE is defined as: “Any untoward medical occurrence in a study patient administered etrasimod which does not necessarily have to have a causal relationship with this treatment.” An AE can therefore be any unfavorable and unintended sign (including an abnormal

laboratory finding), symptom, or disease temporally associated with the use of the study medication, whether or not related to the product. AEs can be any of the following:

- Unfavorable changes in general condition
- Subjective or objective signs/symptoms
- Concomitant disease or accidents
- Clinically relevant adverse changes in laboratory parameters observed in a patient in the course of a clinical study
- Pre-existing conditions which worsen in severity or frequency or which have new signs/symptoms associated with them

Lymphopenia will not be captured as an AE because it is an expected pharmacologic effect of the drug.

AEs will be elicited at the time indicated in the schedule. Any adverse or unexpected events, signs and symptoms will be fully recorded on the AE Form including details of intensity, onset, duration, outcome and relationship to the drug as determined by the PI. Whenever possible, a constellation of signs and symptoms should be recorded as a unifying diagnosis (e.g., self-limited fever, runny nose, cough, and scratchy throat should be captured as an upper respiratory infection rather than by the individual signs and symptoms). AEs may also be reported at any time. The type and duration of follow-up of patients after AEs will be documented.

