6.15.2. Serious Adverse Events and Expedited Reporting of Adverse Events

An SAE is any untoward medical occurrence that at any dose results in the following outcomes:

- Death
- Is life-threatening
- Required/Prolonged hospitalization
- Disability/Incapacity
- Congenital anomaly/birth defect

- Important medical event

SAEs will be captured from the time of ICF signature to 30 days after the last dose of study drug, and will be monitored until resolution or stabilization.

An important medical event that may not result in death, be life-threatening, or require hospitalization may be considered a SAE when, based upon appropriate medical judgment, it may jeopardize the patient and may require medical or surgical intervention to prevent one of the outcomes listed in this definition. Examples of such a medical event includes allergic bronchospasm requiring intensive treatment in an emergency room or at home, blood dyscrasias, or convulsions that do not result in in-patient hospitalization, or the development of drug dependency or drug abuse.

Elective hospitalization and/or surgery for clearly pre-existing conditions (for example a surgery that has been scheduled prior to the patient's entry into the study) will not be reported as a SAE. All other hospitalizations, including elective hospitalizations for any condition that was not pre-existing, will be reported as a SAE.

Any AE considered serious by the investigator or which meets SAE criteria must be reported to PPD Pharmacovigilance (PVG) within 24 hours from the time study site personnel first learn about the event.

The following contact information is to be used for SAE reporting:

EMEA ASIA Safety Central Mailbox: [REDACTED]

Australia: [REDACTED] (tel)

Australia: [REDACTED] (fax)

Or alternatively:

PPD Medical Affairs/Pharmacovigilance

PPD PVG Hotline: (United Kingdom number) [REDACTED] PPD PVG

Fax line: (United Kingdom number) [REDACTED]

A full description of every SAE will need to be provided to PPD PVG (this may be supported by source documentation such as laboratory reports or a discharge summary should the patient be hospitalized).

Other safety issues as defined in ICH Guideline E2A, and EU Eudralex Volume 10 also qualify for expedited reporting. In these situations, the process will be as detailed for SAEs above:

- SAEs which could be associated with the trial procedures;

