7.3. Follow-Up Period

7.3.1. [REDACTED]

[REDACTED] procedures for all subjects are as follows:

- [REDACTED]
- Measure body weight and calculate BMI
- Perform physical exam and neurological exam
- Measure vital signs
- Record any concomitant medications
- Record any AEs
- Obtain blood samples for:
 - Chemistry, including ALP
 - Complete blood count and lymphocyte subsets
 - Total serum IgG and IgM, AMA and hsCRP

If the absolute peripheral lymphocyte count has not recovered to at least 80% of the baseline value, or reached normal ranges at the 2-week follow-up, the subject must return for weekly CBC tests until the absolute peripheral lymphocyte count has returned to at least these values.

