9.7.1. Adverse Events

AEs will be coded using the most current MedDRA and tabulated, including categorical information of interest such as onset and resolution times, time of onset relative to dose, severity at onset, maximum severity, causal relationship to study medication, and action taken. AEs will be regarded as 'pre-treatment' if they occur between screening and the time of administration of the first dose of etrasimod. All other AEs that occur after the first dose of study medication will be considered to be 'treatment-emergent'.

Pre-treatment and treatment-emergent AEs will be listed by patients, in terms of seriousness, severity and intensity (assessed according to the CTCAE v4.03; 14Jun2010 definitions³¹). TEAEs will be classified according to system organ class.

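### Weekly blood counts continue until lymphocytes recover, but planned AE and SAE capture ends at day 30 after the last dose, and the TEAE definitions disagree on events after that

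*Combined protocol and SAP*

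**What the plan says.** **Lymphocyte follow-up.** Section 6.12.1 applies to a patient whose absolute lymphocyte count "has not recovered to at least 80% of the baseline value, or within normal ranges, at the 2-week follow-up (week 26"). In that case "the patient must return for weekly CBCs until the absolute peripheral lymphocyte count has returned to at least these values". Section 7.3.1 repeats the rule: "the subject must return for weekly CBC tests until the absolute peripheral lymphocyte count has returned to at least these values". Neither section gives an end date.

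**AE and SAE windows.** Section 6.15 has patients "monitored from ICF signature to 30 days after the last dose of study drug for AEs". Section 6.15.2 states that "SAEs will be captured from the time of ICF signature to 30 days after the last dose of study drug". In Section 6.15.1, events "up to 30 days after the last medication intake will be presented as treatment emergent AEs (TEAEs"). All three windows are the same for every patient, and no readable text lengthens them when lymphocytes stay low.

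**A second TEAE definition.** Section 9.7.1 reads "All other AEs that occur after the first dose of study medication will be considered to be" treatment-emergent, and Section 8.2.1 says the same. Neither sets an upper time limit.

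**Related rules.** Section 6.15.1 excludes lymphopenia itself from AE recording because it is an expected drug effect. It also lets patients report AEs at any time. Section 6.15.8 arranges follow-up for AEs already present at Week 26.

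**The concern.** The protocol allows for the lymphocyte effect outlasting the two-week follow-up and sets no limit on how long such a patient must keep returning. AE and SAE collection runs on a fixed clock instead. A patient who is slow to recover can therefore attend the site every week for a drug effect after the stated collection period has closed.

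Safety and tolerability are the sole primary objective (Section 2.1), and the drug acts by lowering circulating lymphocytes (Sections 1.2 and 1.3.1). Because lymphopenia is not recorded as an AE, any clinical consequence of prolonged suppression is the only form in which it would appear in the AE data. Missing such events can only lower the recorded count, and it does so in the patients with the longest drug effect.

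The conflicting TEAE definitions add a second problem. Even when a late event is written down, sites and programmers have no single rule for classifying it.

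**Working it through.** No sample size, power or alpha figure bears on this point; Section 9.2 states that there was no formal sample size estimation. The check is calendar arithmetic followed by a comparison of sections.

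**Inputs**
- Last dose: one day before the end-of-treatment visit at Week 24 (Section 3.1).
- Follow-up visit: Week 26, two weeks after the end of treatment (Sections 3.1 and 6.12.1).
- Extra counts: weekly from Week 26 (Sections 6.12.1 and 7.3.1).
- Collection cutoff: day 30 after the last dose (Sections 6.15, 6.15.1 and 6.15.2).

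**Calendar, with the last dose as day 0**
- Week 24 visit = day 1.
- Week 26 visit = 1 + 14 = day 15, which leaves 30 − 15 = 15 days of planned capture.
- Extra count k falls on day 15 + 7k:

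| Extra count | Day after last dose | Within 30 days? |
|---|---|---|
| 1 | 22 | yes |
| 2 | 29 | yes |
| 3 | 36 | no |
| 4 | 43 | no |
| 5 | 50 | no |

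If the last dose were taken on the Week 24 day itself, the first three counts would fall on days 21, 28 and 35. The third is still outside the window.

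**Does another passage cover the time after day 30?**
- Section 7.3.1 lists AE and concomitant medication recording for the follow-up visit, but for the extra returns its readable text mentions only the blood count.
- Section 6.15.8 concerns AEs already present at Week 26, not new ones.
- The follow-up of SAEs to resolution or stabilization in Section 6.15.2 concerns SAEs already captured.
- Spontaneous reporting under Section 6.15.1 remains possible, but it is not planned elicitation.

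**Classification of an event starting on day 36, if recorded**
- Section 6.15.1: 36 > 30, so not a TEAE.
- Sections 8.2.1 and 9.7.1: after the first dose, so a TEAE.

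**Size.** The readable text gives no lymphocyte recovery time and no infection rate, so the number of patients affected cannot be calculated. One patient is 1/20 = 5% of a full study. As an illustration on assumed inputs only, let m patients be unrecovered after day 30, each with infection risk p over the extra time. The chance that at least one infection starts after planned capture has ended is 1 − (1 − p)^m:
- m = 1, p = 0.02: 1 − 0.98 = 2%.
- m = 5, p = 0.10: 1 − 0.90^5 = 41%.

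The width of that range reflects how little the documents say about either input.

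**The case against.** A reader might infer that late infections will go uncounted. The documents do not support that. AEs may be reported at any time under Section 6.15.1. The sentence in Section 6.15.2 requiring serious events to be reported within 24 hours of the site learning of them carries no time limit of its own. A late event that reached the database would also be a TEAE under Section 9.7.1, the analysis section. What is missing is planned elicitation, not every reporting route.

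A reader might also infer that the extra visits collect a blood count and nothing else. That cannot be confirmed. Section 6.15.1 has AEs elicited according to the schedule, and Table 1 is not readable in the public copy. Part of Section 7.3.1 is also redacted.

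Nor do the documents show that anyone would be affected. Section 6.12.1 is a contingency, and returning to the normal range is enough even below 80% of baseline. The 30-day window already runs about 15 days past Week 26 and covers the first two extra counts.

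Finally, ending the TEAE window itself at lymphocyte recovery would make observation time depend on the drug effect. Crude percentages would then mix longer follow-up with higher risk, whereas a fixed window gives patients comparable observation.

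All of this stands. It limits the size of the concern and shapes the remedy. It does not supply AE collection at the later visits or settle the TEAE definitions.

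**Conclusion.** The mismatch holds on the readable text. From about day 36, a patient with unrecovered lymphocytes is under mandatory follow-up with no stated AE or SAE collection. It concerns only events that start after day 30 in patients still unrecovered at that time. Those events may be missed, or may depend on spontaneous reporting. Any loss would lower the recorded event count, but by an unknown amount.

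The inconsistency between Section 6.15.1 and Sections 8.2.1 and 9.7.1 is certain and does not depend on how many patients are affected.

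The conclusion assumes the planned timing of the last dose and the Week 26 visit, and that Table 1 does not already call for AE recording at the extra visits. This is an inexpensive improvement to safety ascertainment; the documents do not show that the safety results would be materially biased.

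**What to change.** 1. In Sections 6.12.1 and 7.3.1, add recording of AEs, SAEs and concomitant medications at each extra weekly CBC visit, and check that Table 1 agrees.
2. In Sections 6.15, 6.15.1 and 6.15.2, extend AE and SAE collection for these patients to the later of day 30 after the last dose and the date of the CBC that meets the recovery criterion.
3. Use one TEAE definition in Sections 6.15.1, 8.2.1 and 9.7.1. Keep the fixed 30-day window for the main TEAE table so that observation time is comparable across patients, and list events after day 30 separately.

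The cost is amendment wording and slightly more data entry. The patients are already attending, so no new visit is needed. Database lock may have to wait for the last unrecovered patient; Section 6.15.8 already provides for deciding whether to hold or later update the database for unresolved AEs.

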6.13. Pharmacokinetic Assessments

Patients will have a serial PK sampling

[REDACTED]
[REDACTED] All PK samples are to be collected [REDACTED] of the scheduled timepoint.

PK data [REDACTED] will support the dose escalation of etrasimod in PBC patients at Week 12. An additional PK blood sample will be collected, if possible, at the time of any intolerable AE (an AE leading to study drug discontinuation) or SAE. Sampling will be performed as outlined in Schedule of Procedures and Visits (Table 1).

At each PK time point, approximately 2 mL of blood will be collected, and the plasma will be harvested. Plasma samples will be shipped to the analytical lab for analysis of etrasimod and its putative metabolites (if possible). After the completion of study, samples will be transferred to sponsor designated storage site in US, and retained for future exploratory research related to the study drug. In general, the storage time is no more than 3 years. A PK sample collection manual will be provided to instruct the type of anticoagulant, the material supplies, sample processing, storage and shipping procedures.

6.14. C4 and [REDACTED]

C4 and [REDACTED] may be analyzed, if deemed necessary by the Sponsor, depending on ALP levels throughout the course of the study for exploratory objectives. For this purpose, back up PK samples will be used.

6.15. Adverse Events Assessments

Patients will be monitored from ICF signature to 30 days after the last dose of study drug for AEs to the study drug and/or procedures.

AEs will be recorded and reported in accordance with ICH GCP. The definitions of AEs and serious AEs (SAEs) will be as given in ICH Guideline E2A, “*Clinical Safety Data Management: Definitions and Standards for Expedited Reporting*.” The outcome of an AE will be defined according to ICH Guideline E2B(R3), “*Clinical Safety Data Management: Data Elements for Transmission of Individual Case Safety Reports*.” The relationship to investigational product will be classified using World Health Organization (WHO) criteria.

